2.2.3. Minimization of Risks

Research participants will be carefully screened to meet enrollment criteria. Participants meeting exclusion criteria will not be enrolled. The study participant informed consent will be presented with clear description of the study requirements and opportunity to have questions answered before enrollment. Once an event occurs, review of symptoms will be ascertained at onset, 15, 30, and 60 minutes. Reporting of adverse events will be reviewed routinely and in accordance with regulatory guidelines (21CFR, GCP) by the Principal Investigator. Participants with occurrence of worsening symptoms or adverse

events will be advised to stop taking the test product, may seek medical attention, and exit the study.

3. Study Objectives

The purpose of the present study is to evaluate 1) the impact of the test product on symptoms of occasional indigestion and heartburn in 200 adult participants who suffer from occasional indigestion and heartburn and 2) the subjective experience of these participants related to general health, indigestion and heartburn symptoms, and personal experience with the test product.

This will be evaluated based on the primary and secondary endpoints. These endpoints, the analysis populations, and their respective measures are described below. Further details on the methods for measuring the outcomes can be found in the Study Outcome Measures and Analysis Plan sections.

Primary Endpoint:

The primary endpoint has two components, reduction in indigestion severity and reduction in heartburn severity. Participants will be asked to rate each symptom (bloating, early fullness during a meal, pain or discomfort in the upper abdomen, burning in the upper abdomen, pain/burning in the center of your chest, nausea, vomiting, and burping) on a 4-point scale at 4 time points: prior to taking the test product, 15, 30, and 60 minutes after taking the test product. The improvement in symptoms from baseline will be evaluated on a pairwise basis separately for each component and each time point. P-values will be computed for the improvement. Given that indigestion can impact an individual's quality of life, the primary endpoint was chosen to see the test product's effects on symptoms. [1, 9, 12]

Secondary Endpoint:

Secondary endpoints will be analyzed to evaluate safety and patient satisfaction with relief of symptoms. These include:

- The time to other intervention will be analyzed.

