4.2. Required Behavior

During the hour directly following consumption of the test product, no medication or supplementation (including all CBD products) other than the test product should be taken

for relief of indigestion and heartburn symptoms. Once the 1-hour report has been recorded the participant may take other medications or supplements. If medication is taken, the participant will record this in their symptom diary.

Participants are asked to limit the consumption of alcohol beverages to less than or equal to two drinks per day.

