6.2. Study Schedule of Activities

Assessments	Screening	Consent	Before Receipt of Test Product	Test Product Received	Event 1	15 Minutes After Event Start	30 Minutes After Event Start	60 Minutes After Event Start
Study Window								
Screening Survey	X							
Consent		X						
Baseline Survey			X					
Demographics			X					
Acknowledgement of receipt of test product				X				
Symptom Diary					X			X
4-point Likert Scale					X	X	X	X
Test Product Consumed					X			
Medications & Supplements			X					
AE Assessment					X	X	X	X
Study Exit Survey								

Assessments	Event 2	15 Minutes After Event Start	30 Minutes After Event Start	60 Minutes After Event Start	Event 3	15 Minutes After Event Start	30 Minutes After Event Start	60 Minutes After Event Start	Study Exit
Study Window									
Screening Survey									
Consent									
Baseline Survey									
Demographics									
Acknowledgement of Receipt of Test Product									
Symptom Diary	X			X	X			X	
4-point Likert Scale	X	X	X	X	X	X	X	X	
Test Product Consumed	X				X				
Medications & Supplements									
AE Assessment	X	X	X	X	X	X	X	X	X
Study Exit Survey									X

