6.4. Adverse Event and Safety Monitoring

Adverse Events (AEs) are defined as any untoward medical occurrences described by the study participant. All AEs will be self-reported and documented on the platform. The AEs will be reviewed by the study team including the remote trial coordinator and study principal investigator and reported according to the IRB requirements. Participants who experience adverse events will be advised to seek medical attention.

In the event that a participant experiences an adverse event, the clinical study manager or clinical ops coordinator will notify both the PI and Sponsor. The Sponsor will take appropriate action according to their standard operating procedures for any adverse events that warrant action by the sponsor.

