13.1.5. Appendix E Symptom Diary

Please complete the following items during your first episode of Indigestion/Heartburn. We encourage you to complete the forms online in real time. However, if you cannot log into your patient portal at the time of your symptoms please complete these forms and log into your patient portal as soon as possible and complete the online forms.

Reminder: Do not take any other medications or supplements within the first hour of taking the test product.

Date of Onset:	Ti	me of Onset:	
Trigger (check all that apply Food □ Caffeine □ Alcol □ Smoking □Other:	nol		
Time test product taken:			
Please rate the followin answer.	g symptoms at th	e following time point	s. Circle one
Onset (Prior to Bloating 0 No Symptom		2	3
No Symptom	Slight	Moderate	Severe

Early Fullness During a 1	Meal	2	3			
No Symptom	Slight	Moderate	Severe			
Pain or Discomfort in the	e Upper Abdomen	2	3			
No Symptom	Slight	Moderate	Severe			
Burning in the Upper Ab		2	2			
0 No Symptom	1 Slight	2 Moderate	3 Severe			
Pain/Burning in the center	er of your chest					
0 No Symptom	l Slight	2 Moderate	3 Severe			
J 1	S					
Nausea						
0 No Symptom	1 Slight	2 Moderate	3 Severe			
1 to Symptom	Siigiit	Woderate	Severe			
Vomiting						
0 No Symmton		2 Madamata	3			
No Symptom	Slight	Moderate	Severe			
Burping						
0	1	2	3			
No Symptom	Slight	Moderate	Severe			
Other						
0	1	2	3			
No Symptom	Slight	Moderate	Severe			
15 Minutes after taking the test product						
Bloating						
0	1 Slight	2 Moderate	3 Sayara			
No Symptom	Slight	Moderate	Severe			

Early Fullness During a Meal 0 1 2 3							
No Symptom	Slight						
Pain or Discomfort in the	Upper Abdomen	_	_				
0	I C1: 14	2	3				
No Symptom	Slight	Moderate	Severe				
Burning in the Upper Abo	lomen						
0	1	2	3				
No Symptom	Slight	Moderate	Severe				
Pain/Rurning in the center	r of vour chost						
Pain/Burning in the cente	1	2	3				
No Symptom	Slight	Moderate	Severe				
- · · · · · · · · · · · · · · · · · · ·	38		20100				
Nausea							
0	1	2	3				
No Symptom	Slight	Moderate	Severe				
Vomiting		_	•				
0	l C1: 14	2	3				
No Symptom	Slight	Moderate	Severe				
Burping							
0	1	2	3				
No Symptom	Slight	Moderate	Severe				
Other:							
0	1	2	3				
No Symptom	Slight	Moderate	Severe				
30 Minutes after taking the test product							
Bloating							
0	1	2	3				
No Symptom	Slight	Moderate	Severe				

Early Fullness During a M	Meal		3		
0 No Symptom	2				

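### The diary reminder bars every other medicine for an hour after dosing: it drops Section 4.2's limit to indigestion and heartburn remedies and makes no exception for treating an adverse event

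*Combined protocol and SAP*

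**What the plan says.** Appendix E, the diary kept during an episode, states: "Reminder: Do not take any other medications or supplements within the first hour of taking the test product". It gives no purpose for the medicine and no exception.

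Section 4.2 of the protocol sets the rule for the hour after dosing: "no medication or supplementation (including all CBD products) other than the test product should be taken", and the sentence continues "for relief of indigestion and heartburn symptoms. Once the 1-hour report has been recorded the participant may take other medications or supplements". The first sentence therefore limits the bar by purpose. The second, which lifts it after the one-hour report, does not repeat that limit. Sections 4 and 6.1 speak of alternative treatment being allowed after an hour, and Section 6.1 asks for any other medication to be written in the diary.

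On adverse events, Section 2.2.3 says that participants with worsening symptoms or adverse "events will be advised to stop taking the test product, may seek medical attention, and exit the study". Section 6.4 says "All AEs will be self-reported and documented on the platform" and "Participants who experience adverse events will be advised to seek medical attention". In Section 6.2 the row "AE Assessment" is marked at onset, 15, 30 and 60 minutes of each of three episodes, and at study exit. If there is a side effect, the diary sends the participant to the adverse event form in Appendix G. That form asks what was done to relieve it and whether a doctor or hospital was needed.

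**The concern.** The diary is the instruction in front of the participant at the moment it matters: during the episode, at home, with no clinician present. It is also issued on paper for use when the portal cannot be reached. Taken at its word, the reminder tells someone with hives or wheezing twenty minutes after the capsules not to take an antihistamine or an inhaler until the hour is up. It would also cover a routine medicine for an unrelated condition. The first sentence of Section 4.2 asks for neither.

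At stake is a possible delay in treating a reaction, plus a participant instruction stricter than the rule it is meant to repeat. The primary endpoint, the sample size and the test are not affected.

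**Working it through.** The check is mainly a comparison of wording; the only arithmetic is a count of scheduled assessments.

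**Scope of the bar, side by side**

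| Place | What is barred in the first hour | Limited by purpose? | Exception for an adverse event? |
|---|---|---|---|
| Section 4.2, first sentence | Medication or supplements other than the test product | Yes: indigestion and heartburn relief | Not needed; treating a reaction is outside the limit |
| Section 4.2, second sentence | Implied: other medicines are allowed once the one-hour report is in | No | None |
| Section 6.1 | Alternative medicines or supplements | Only through the word alternative | None |
| Appendix E reminder | Any other medicine or supplement | No | None |

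The reminder is broader than the first sentence of Section 4.2 and about as broad as the second. Sections 2.2.3 and 6.4 give advice about adverse events, but neither mentions the one-hour bar. Because adverse events are self-reported on the platform, that advice follows a report. The supplied adverse event form has five questions. Its questions on relief and medical care assume that treatment happens, but none of them lifts the bar.

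**Adverse event assessments relative to the hour (Section 6.2)**

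| Time | Per episode | Three episodes |
|---|---|---|
| Onset | 1 | 3 |
| 15 minutes | 1 | 3 |
| 30 minutes | 1 | 3 |
| 60 minutes | 1 | 3 |
| Study exit | – | 1 |

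- Total: 3 × 4 + 1 = 13.
- At 15, 30 or 60 minutes: 3 × 3 = 9 of 13. Six of these (15 and 30 minutes) lie inside the hour and three (60 minutes) at its end.
- The three onset assessments are left out, because the diary takes its onset rating before the product is swallowed.

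**Exposure to the rule.** Participation ends after three recorded episodes, so the bar covers at most 3 × 1 = 3 hours per participant.

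**Type of reaction.** Section 6.4.1 lists 10 anticipated events. Three are allergic in type (hives, difficulty breathing, facial swelling), and all 10 are tied to doses above recommended use. The documents give no rate at the study dose.

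**Recording.** The row "Medications & Supplements" in Section 6.2 is marked once, before the product arrives. During an episode, the record of other medicines is the diary's own medication lines (name, dose, time), which follow a question about needing another medication.

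**The case against.** The strongest reply is that nobody is told to leave a reaction untreated. Adverse events have their own path: stop the product, seek medical attention, leave the study. The form that the diary points to asks what the participant did about the side effect and whether a doctor or hospital was involved, which makes sense only if treatment is expected. The line is headed as a reminder, so it restates a rule rather than creating one. It sits in a diary about indigestion episodes whose other medication questions concern rescue. Known allergy to an ingredient is an exclusion. The consent, information sheet, portal FAQs and product insert are outside the text reviewed and may carry emergency instructions.

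Most of this stands, and it is why the point is minor. What remains is that none of the supplied text lifts the diary's bar, and the reminder does not faithfully repeat the first sentence of Section 4.2.

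Four stronger readings are tempting, and the documents do not support them:

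- A reader might infer that the plan forbids treating a reaction. Sections 2.2.3 and 6.4 and Appendix G point the other way.
- A reader might infer that the protocol body is clean and only the diary is at fault. The second sentence of Section 4.2 has no limit by purpose either.
- A reader might count 12 of 13 adverse event assessments as falling in the barred hour. That includes the three at onset, where the diary rating comes before dosing.
- A reader might infer that a medicine taken for another reason would distort time to other intervention, or that recording a reason would prevent this. The documents do not define that endpoint closely enough to say either.

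**Conclusion.** The point holds as a minor wording correction for participant safety. The reminder omits the limit stated in Section 4.2 and has no exception for an adverse event. Nine of 13 scheduled adverse event assessments fall inside or at the end of the hour it governs, for at most three hours per participant. These figures describe the overlap in time; they do not measure risk. Few participants are likely to be affected, given the tie to high doses, the allergy exclusion and the natural reading of the line, but that is a judgement and not an estimate.

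The conclusion assumes that the portal version of the diary carries the same line as the supplied form. An exception elsewhere in the participant materials would lower the risk further but would not correct this line.

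**What to change.** Replace the Appendix E reminder, in both the portal and paper forms, with wording such as:

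> For one hour after taking the test product, do not take any other medication or supplement to relieve indigestion or heartburn. This does not apply to treating a side effect: if you have hives, swelling, wheezing or difficulty breathing, do not wait; get medical help at once. Record anything you take.

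Add the indigestion and heartburn limit to the second sentence of Section 4.2 as well, so that the body and the diary agree.

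The cost is one diary line in two formats and a short insertion in Section 4.2; the analysis does not change. The request to record matches what Section 6.1 already asks. The downside is that a medicine taken in the hour for another reason, such as a painkiller or an antiemetic, could shift a pain or nausea score in a study with no control group. The record does not remove that effect, but it makes it visible.

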- After completing the surveys, the participant will take the test product. The participant will take
 2 capsules per indigestion and heartburn episode. With a max of 6 capsules per day. (If
 participant takes 6 capsules in 1 day this will be defined as 3 indigestion and heartburn episodes
 and the participant will be exited from the study).
- After taking the test product, the participant will complete a 4-point Likert scale assessment for each symptom at 15 minutes, 30 minutes, and 1 hour after taking the test product.
- When the participants symptoms have resolved , the participant will complete the symptom diary.
- If the participant takes any other medication outside of the test product, the participant will record this on the symptom diary.
 - The participant is allowed to take alternative medications or supplements AFTER 1 hour from taking the test product.
- After taking the test product, the participant will be instructed to fill out an Adverse Event form for any side-effects experienced.
- After the first episode of indigestion and heartburn, the participant will be asked to complete the same process for another 2 episodes within the 60-day study time frame; however, these are not required.
- If the participant completes the required assessments for a total of 3 episodes of indigestion and heartburn, they will be prompted, by email, to exit the study.
- If the participant only completes the required assessments for the required 1 episode of indigestion and heartburn, the participant will be prompted, by email, to complete the study exit form and will be exited from the study on day 60 (60 days from the day of receipt of the test product).
- Neither the sponsor nor Hawthorne Effect Inc. will not collect any unused test product.
- Upon receipt of study exit survey and review of completed study forms, participant will receive an Amazon gift card of \$25 via email.

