13.1.4. Appendix D Baseline Form

Baseline

 Demograph 	ics
-------------------------------	-----

- a. Race/Ethnicity (Black or African American, White, Asian, American Indian or Alaska Native, Native Hawaiian or another pacific islander, other: _____, do not want to share)
- b. Sex (M, F, or Do not want to share)
- 2. On average how often do you get Indigestion and Heartburn? (few times a year, once a month, A few times a month, once a week, 2-3 times a week, Everyday)
- 3. How long does it usually take for your symptoms to reach maximum intensity? (0-30 min, 31 min- 1 hour, +1 hour)
- 4. How long do your symptoms usually last without medication? (0-30 min, 31 min- 1 hour,, 1-2 hour, >2 hours, do not resolve)
- 5. How long do your symptoms usually last with medication? (0-30 min, 31 min- 1 hour,, 1- 2 hour, >2 hours, Do not resolve)
- 6. On average how bad are your symptoms without medication? (1-10)
- 7. On average how bad are your symptoms with medication? (1-10)
- 8. What symptoms do you experience when you are having an episode of Heartburn/Indigestion? (Check all that apply)
 - a. bloating
 - b. early fullness during a meal
 - c. pain or discomfort in the upper abdomen
 - d. burning in the upper abdomen
 - e. pain/burning in the center of your chest
 - f. nausea
 - g. vomiting
 - h. burping
 - i. other:
 - j. None of the above
- Do any of the following bring on or trigger your symptoms of indigestion or heartburn? (Check All That Apply)
 - a. Overeating
 - b. Eating too quickly
 - c. Fatty/greasy foods
 - d. Spicy foods
 - e. Caffeine
 - f. Alcohol
 - g. Smoking
 - h. Other:
 - i. None of the above

- 10. Do you take medications to treat your symptoms? (yes/no)
 - a. What medication do you take? (free response)
 - b. how long do you wait before taking medication?
 - i. Right away
 - ii. Within an hour
 - iii. 1-2 hours
 - iv. >2 hours

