Dain or Discomfort in the	Unner Abdemen				
Pain or Discomfort in the	Opper Abdomen	2	3		
No Symptom	Slight	Moderate	Severe		
Burning in the Upper Ab	domen				
0 No Symptom	1 Slight	2 Moderate	3 Severe		
Pain/Burning in the center	er of your chest				
0	1	2	3		
No Symptom	Slight	Moderate	Severe		
Nausea					
0	1	2	3		
No Symptom	Slight	Moderate	Severe		
Vomiting					
0	1	2	3		
No Symptom	Slight	Moderate	Severe		
Burping					
0	1	2	3		
No Symptom	Slight	Moderate	Severe		
Other:	1	2	3		
0 No Symptom	Slight	Moderate			
No Symptom	Stight	Woderate	Severe		
60 Minutes afte	er taking the	e test product			
Bloating					
0	1	2	3		
No Symptom	Slight	Moderate	Severe		

Early Fullness During a Meal 0 No Symptom	1 Slight	2 Moderate	3 Severe		
Pain or Discomfort in the Upp 0 No Symptom	oer Abdomen 1 Slight	2 Moderate	3 Severe		
Burning in the Upper Abdom 0 No Symptom	en 1 Slight	2 Moderate	3 Severe		
Pain/Burning in the center of 0 No Symptom	your chest 1 Slight	2 Moderate	3 Severe		
Nausea 0 No Symptom	1 Slight	2 Moderate	3 Severe		
Vomiting 0 No Symptom	1 Slight	2 Moderate	3 Severe		
Burping 0 No Symptom	1 Slight	2 Moderate	3 Severe		
Other: 0 No Symptom	1 Slight	2 Moderate	3 Severe		
After your symptoms resolveplease complete any of the following questions if applicable.					
Did your symptoms resolve completely with the test product? Yes No Time of complete symptom resolution:					

Did you need to take another medication	on: Yes N	No
Medication #1:	Dose:	Time:
Medication #2:	Dose:	Time:
Medication #3:	Dose:	Time:
Did your symptoms resolve completely	with taking your altern	native medication? Yes No
After taking the alternative medication,	, time of complete resol	lution of symptoms:

Did you experience any side effects after taking the test product? (Y/N) If yes, **Please fill out** the Adverse Event form.

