13.1.6. Appendix F Study Exit Form

for your symptoms? (y/n)

Study Exit

	1. Please rate your overall experience with the test product.											
Po	0 oor		1	2	3	4	5 Neutral	6	7	8	9	10 Excellent
	1a.	Wł	ny? (f	ree res	sponse)							
	2.	Do	you f	feel th	at the t	est pr	oduct helpe	d wit	th your	indiges	tion a	and heartburn?
No	0 ot at		1	2	3	4	5 Neutral	6	7	8	9	10 definitely
	3.	Но	w like	ely are	you to	recon	nmend the t	est p	roduct	to your	frien	ds or family members?
No	0 t Li		1	2	3	4	5 Neutral	6	7	8	9	10 Extremely Likely
	4.		-			-	oduct helpe and upset s	-	-	cope w	ith o	ccasional heartburn,
No	0 ot at		1	2	3	4	5 Neutral	6	7	8	9	10 definitely
	5.			•	_		you would li stency, or o				•	vour experience with the ponse)
	6.	Dic	the t	test pr	oduct h	nelp p	revent you f	rom	having	to take	any a	alternative medication

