13.1.7. Appendix G Adverse Event Form

Upset Stomach AE document

- 1. Did you experience any side effects after taking the test product? Y/N
 - a. If so, did you experience any of the following
 - o itching, rash, hives, throat/lip/tongue swelling, wheezing
 - low blood pressure, fainting, chest pain, shortness of breath, palpitations, irregular heart beat
 - o severe, persistent nausea, vomiting, diarrhea, or abdominal pain
 - o difficulty urinating, decreased urination
 - o fatigue, appetite loss, yellowing skin/eyes, itching, dark urine
 - severe joint/muscle pain
 - o slurred speech, one-sided weakness of face, arm, leg, vision
 - o abnormal bleeding from nose or gums
 - o blood in urine, stool, vomit,
 - o marked mood, cognitive, or behavioral changes, thoughts of suicide
 - o Other:
- 2. Please give a description of the event
- 3. How soon after taking the test product did you experience the side effect?
- 4. What did you do to alleviate the side effect?
- 5. Did you have to go to the hospital or see a doctor for this side effect?
 - a. Please describe any diagnosis or treatment that they provided.
 - b. If you were seen in the hospital, please upload any discharge paperwork or other documents from the hospital.

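### The schedule marks AE assessment at every time point and at exit, but the diary asks once per episode, under a heading conditional on symptom resolution, and the exit form does not ask

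*Combined protocol and SAP*

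**What the plan says.** **Schedule (section 6.2).** The row "AE Assessment" is marked at event start and at 15, 30 and 60 minutes for each of Events 1, 2 and 3, and again at study exit. The exit survey is a separate row.

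**Diary (Appendix E).** The pages for onset, 15, 30 and 60 minutes hold symptom ratings only. A final block follows, headed "After your symptoms resolveplease complete any of the following questions if applicable". It asks whether and when symptoms resolved and what other medication was taken. Its last item is the diary's only AE prompt: "Did you experience any side effects after taking the test product? (Y/N) If yes", with a pointer to the AE form.

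**Procedures (section 6.1).** The resolution trigger is repeated: "When the participants symptoms have resolved , the participant will complete the symptom diary". A separate instruction does not depend on resolution: "After taking the test product, the participant will be instructed to fill out an Adverse Event form for any side-effects experienced".

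**AE form (Appendix G).** It opens with "Did you experience any side effects after taking the test product? Y/N". It asks how long after dosing the event began, but has no field for the episode or the scheduled time point.

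**Exit form (Appendix F).** It starts with "Please rate your overall experience with the test product" and continues through six items on satisfaction, perceived benefit, recommendation, comments and avoidance of other medication. None asks about adverse events.

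**Use of the data.** Section 6.4 makes AE reporting entirely self-report. Section 7.1 lists the AE summary among the secondary endpoints.

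**The concern.** The study has no clinic visits (section 4), and section 11 concedes that symptoms get no medical review. What the forms ask, and when, therefore largely determines what AE data exist. Two features of the layout weaken that.

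First, most scheduled assessments have no matching question in the diary or exit form, so it is unclear what would count as having done them. Second, the one routine question sits behind a condition on the course of symptoms. A participant whose symptoms persist is not told to open that block, and its heading makes each item optional. The plan expects that such people exist: the baseline question "How long do your symptoms usually last without medication? (0-30 min, 31 min- 1 hour,, 1-2 hour, >2 hours, do not resolve" offers non-resolution as an answer. Section 6.4.1 lists upset stomach and vomiting among the anticipated AEs, so someone made worse by the product could be both a non-resolver and an AE case.

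At stake is the completeness of the safety summary, and whether silence in the data can be read as absence of events.

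**Working it through.** The plan states no figure on this point, so the check is a count of schedule marks against form prompts.

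**Inputs**
- AE marks per event: 4 (onset, 15, 30, 60 minutes), from section 6.2.
- AE marks at exit: 1, from section 6.2.
- AE prompts in the diary: 1 per episode, from Appendix E. This assumes the same diary is repeated for later episodes, as section 6.1 implies.
- AE prompts in the exit form: 0, from Appendix F.

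**Formulas** for k episodes
- Marks = 4k + 1
- Prompts in diary and exit form = k
- Marks without a prompt = (4k + 1) − k = 3k + 1

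| Episodes | Marks | Prompts | Marks without a prompt |
|---|---|---|---|
| 1 | 4 + 1 = 5 | 1 | 4 of 5 |
| 3 | 12 + 1 = 13 | 3 | 10 of 13 |

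**Leaving out onset.** The onset page is completed before the product is taken, so a side-effect question about that dose cannot apply there. Without the onset marks the count is 3k + 1 marks against k prompts: 4 against 1 for one episode (3 without a prompt) and 10 against 3 for three episodes (7 without). The mismatch shrinks but remains.

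**Appendix G.** It is not in these counts because no section says when it is presented. It could in principle serve any of the marks. As section 6.1 describes it, the participant completes it when something has happened. A participant with no side effects need not open it, and then no negative answer is stored. A missing form could mean no event, an event not reported, or a participant who stopped responding.

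**Who is exposed.** On the literal heading, anyone whose symptoms end, whether early, late, spontaneously or after other medication, reaches the diary question. Those who may not reach it are participants whose symptoms never resolve. The share of participants without a routine AE answer would be roughly

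P(never resolves) × P(leaves the block blank, given never resolves).

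The documents give neither probability, so no number can be put on it.

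**The case against.** The strongest case on the other side has five parts.

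- **Appendix G exists.** It has its own Y/N, which would be redundant if the form were opened only after a positive diary answer, and the instruction in section 6.1 follows dosing, not resolution. This stands against any claim that the diary question is the only AE prompt. It does not supply the missing link to the scheduled times.
- **Exit.** AE assessment and the exit survey are separate rows in section 6.2, so the lack of an AE item in Appendix F does not prove that no exit assessment was planned. That is correct. But no document says how it is done.
- **The block includes non-resolvers.** It asks whether symptoms resolved with the product and, later, with other medication, and a participant may answer no to both. Section 6.2 also marks the diary at 60 minutes whatever the symptom status. This shows the authors probably meant the block for everyone. The heading and section 6.1 still say otherwise.
- **Other safeguards.** A coordinator may chase incomplete forms (section 6.3), and the gift card follows review of the forms (section 6.1). Nausea, vomiting, abdominal pain and a write-in symptom are rated at each time point, so some gastrointestinal worsening is recorded anyway. These reduce the risk but do not replace a recorded AE answer.
- **Portal.** The appendix has a paper layout, and the electronic portal may prompt differently. No such prompt is described.

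A reader might infer more: that AE ascertainment follows the efficacy result, so that people who do not improve are not asked, or that a blank answer will be tabulated as no event. The documents support neither. Failing to improve by 60 minutes is not the same as never resolving, and late resolvers still reach the question. No rule for unanswered AE items is stated, and section 7.3 leaves analysis detail to a later SAP.

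**Conclusion.** There is a mismatch between schedule and forms, and it should be corrected. Section 6.2 marks 13 AE assessments for a three-episode participant and 5 for a one-episode participant. The diary supplies 3 and 1 prompts, each under a resolution-conditional and optional heading, and the exit form supplies none. Appendix G partly fills the gap, but it is tied to no scheduled time point and works by exception.

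The consequence is a risk of under-ascertained AEs, mainly in participants whose symptoms never resolve. That direction is inferred from the form layout, and it assumes that the portal follows the appendices. Its size cannot be computed, because the documents give no rates of resolution or form completion; a count of affected participants would be guesswork. AEs are a descriptive secondary endpoint, so the primary analysis and the sample size are unaffected.

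**What to change.** 1. Move the side-effect Y/N out of the post-resolution block and make it a required item on the 60-minute diary page, for every episode and whatever the symptom status.
2. Add a required Y/N at study exit, either as an item in Appendix F or by stating that Appendix G is administered then.
3. Reconcile the onset, 15- and 30-minute AE marks in section 6.2 with the forms: add the question to those pages or remove the marks. State in section 6.1 when Appendix G is presented, and add a field for the episode it refers to.
4. State in the SAP that unanswered AE items are reported as missing, with the number who answered shown beside the number treated.

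Cost: edits to the diary and exit forms, one field on the AE form, one schedule row and a sentence or two of text. Participants spend a few more seconds, and the study team will have a few more minor reports to review.
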